7.1.2 Guidelines for Management of Adverse Events

Adverse events related to radiation therapy will be managed at the discretion of the treating radiation oncologist, per institutional standards.

7.2 Supportive Care

All supportive measures consistent with optimal subject care may be given throughout the study.

7.3 Contraception

Subjects who have not had surgical removal of their prostate and have a partner of child bearing potential must agree to use condoms beginning at the signing of the ICF until at least 6 months after the last dose of study treatment. Because of the potential side effect on spermatogenesis associated with radiation, female partners of childbearing potential must agree to use a highly effective contraceptive method during and for 6 months after completing treatment.

8 STUDY CALENDAR

8.1 Arm A

Procedures	Screening ¹ (-4 weeks)	On Treatment		Follow-up ²	
		Salvage Therapy	Response Assessment ³ (45 days ± 5 days after last day of RT)	Year 1 (Q3M ± 2 weeks)	Year 2-3 (Q3M ± 1 month)
		Radiation			
Informed Consent	X				
Medical History ⁴	X				
Eligibility Criteria	X				
Clinical Assessments					
Vital Signs, Weight ⁵	X		X	X	X
Physical Exam	X		X	X	X
ECOG Performance Status	X		X	X	X
Adverse Event Collection ⁶		At each visit			
Concomitant Medication Collection	X	At each visit			
Laboratory Studies					
Hematology ⁷	X				
Chemistry ⁸	X				
LDH	X				
PSA ⁹	X		X	X	X
Disease Assessments					
Molecular imaging (e.g., fluciclovine PET/CT or PSMA PET/CT scan or other per PI discretion) ¹⁰	X				
CT Scans				X ¹¹	X ¹¹
Nuclear Medicine Bone Scans (if clinically indicated)	X			X ¹²	X ¹²
TRUS Biopsy ¹³	X				
Intervention					
SBRT or Hypofractionated Bone Radiotherapy		X			
Correlative Studies					
Optional Blood ¹⁴	X	X	X ¹⁵		
Optional Archival Tissue ¹⁶	X				
Optional Fresh Tissue ¹⁷	X				
Questionnaires					
PRO and QOL Questionnaires ¹⁸	X		X	X	X
RTOG Toxicity Evaluation ¹⁹			X	X	X

¹ All pre-study/screening procedures should be completed within 4 weeks of study enrollment - with the exception of laboratory tests which need to be completed within 2 weeks prior to study enrollment, and imaging assessments which must be completed within 90 days of enrollment.

² Follow-up procedures will occur every 3 months for 3 years beginning from the last day of RT unless stated otherwise.

³ The response assessment visit will take place 45 ± 5 days after completion of salvage therapy (surgery and/or radiation).

⁴ To include Charlson Comorbidity Index (See Appendix E)

⁵ Vital signs include systolic/diastolic blood pressure, heart rate, respiration rate, pulse oximetry, and body temperature. Height will be captured at screening only.

⁶ Adverse events will be assessed after treatment has begun and at each time a patient is seen in clinic or scheduled for correlative sample collections. Adverse events will be collected every three months for one year after treatment discontinuation.

⁷ Hematology includes CBC with differential and platelets.

⁸ Chemistry includes sodium, potassium, chloride, carbon dioxide or bicarbonate, blood urea nitrogen (BUN), creatinine, glucose, total protein, albumin, calcium, AST, ALT, alkaline phosphatase, total bilirubin.

⁹ PSA progression must be confirmed according to PCWG3 criteria, after at least 1 week. See Section 10.2.1.

¹⁰ To be performed at screening (within 90 days prior to enrollment).

¹¹ CT scans of the chest/abdomen/pelvis scans recommended to be performed 6 months and 1 year after completion of ALL treatments (salvage and adjuvant therapy) (\pm 2 weeks), and annually for 2 additional years (\pm 1 month) in patients without evidence of disease progression, otherwise as clinically indicated.

¹² Nuclear medicine bone scans recommended to be performed 6 months and 1 year after completion of ALL treatments (salvage and adjuvant therapy) (\pm 2 weeks), and annually for 2 additional years (\pm 1 month) in patients without evidence of disease progression, otherwise as clinically indicated.

¹³ TRUS biopsy must be performed at screening (within 1 year prior to enrollment) only for subjects who have been previously treated with definitive prostate radiotherapy and have disease recurrence in the prostate evidenced by positive molecular imaging (e.g., fluciclovine PET/CT or PSMA PET/CT scan or other per PI discretion).

¹⁴ Optional blood draws may be performed prior to starting salvage therapy, at the next standard of care follow up visit after completion of salvage therapy, and at the time of confirmed PSA progression or radiological progression. See Section 14.3 for details.

¹⁵ After completion of salvage treatment, optional blood will only be collected once at time of confirmed disease progression.

¹⁶ Optional archival tissue may be collected at baseline for all subjects for whom it is available. Archival tissue slides should not be cut until requested from the Central Lab. Lack of archival tissue will not be exclusionary.

¹⁷ Optional fresh tissue may be collected prior to starting salvage therapy during the TRUS biopsy (if performed) and at the time of oligometastasectomy or prostatectomy (if indicated and if available after SOC tissue collection). See Section 14.1 and 14.2 for details.

¹⁸ Quality of life (QOL) questionnaires (FACT-P and Expanded Prostate Cancer Index Composite EPIC-26) will be collected prior to starting salvage therapy, at the Response Assessment Visit, and at each follow-up visits. See Appendices C and D.

¹⁹To be performed at the Response Assessment Visit and at each follow-up visits See Appendix A.

8.2 Arm B

Procedures	Screening ^a (-4 weeks)	On Treatment			Follow-up ^b	
		Salvage Therapy	Response Assessment ^c (45 days \pm 5 days after last day of RT)	Adjuvant Radiotherapy ^d (within 4 months after completion of salvage therapy)	Year 1 (Q3M \pm 2 weeks)	Year 2-3 (Q3M \pm 1 month)
Informed Consent	X					
Medical History ^d	X					
Eligibility Criteria	X					
Clinical Assessments						
Vital Signs, Weight ^e	X		X		X	X
Physical Exam	X		X		X	X
ECOG Performance Status	X		X		X	X
Adverse Event Collection ^f		At each visit				
Concomitant Medication Collection	X	At each visit				
Laboratory Studies						
Hematology ^g	X					
Chemistry ^h	X					
LDH	X					
PSA ⁱ	X		X		X	X
Disease Assessments						
Molecular imaging (e.g., fluciclovine PET/CT or PSMA PET/CT scan or other per PI discretion) ^j	X					
CT Scans					X ^k	X ^k
Nuclear Medicine Bone Scans (if clinically indicated)	X				X ^l	X ^l
TRUS Biopsy ^m	X					
Intervention						
Oligometastasectomy		X				
Salvage Prostatectomy ⁿ		X				
Nodal IMRT ^o				X		
Correlative Studies						
Optional Blood ^p	X	X	X	X ^q		
Optional Archival Tissue ^r	X					
Optional Fresh Tissue ^s	X					
Questionnaires						
PRO and QOL Questionnaires ^t	X		X		X	X
RTOG Toxicity Evaluation ^u			X		X	X

^a All pre-study/screening procedures should be completed within 4 weeks of study enrollment - with the exception of laboratory tests which need to be completed within 2 weeks prior to study enrollment, and imaging assessments which must be completed within 90 days of enrollment.

^b Follow-up procedures will occur every 3 months for 3 years beginning from the last day of RT unless stated otherwise.

^c The response assessment visit will take place 45 ± 5 days after completion of salvage therapy (surgery and/or radiation).

^d To include Charlson Comorbidity Index (See Appendix E)

^e Vital signs include systolic/diastolic blood pressure, heart rate, respiration rate, pulse oximetry, and body temperature. Height will be captured at screening only.

^f Adverse events will be assessed after treatment has begun and at each time a patient is seen in clinic or scheduled for correlative sample collections. Adverse events will be collected every three months for one year after treatment discontinuation.

^g Hematology includes CBC with differential and platelets.

^h Chemistry includes sodium, potassium, chloride, carbon dioxide or bicarbonate, blood urea nitrogen (BUN), creatinine, glucose, total protein, albumin, calcium, AST, ALT, alkaline phosphatase, total bilirubin.

ⁱ PSA progression must be confirmed according to PCWG3 criteria, after at least 1 week. See Section 10.2.1.

^j To be performed at screening (within 90 days prior to enrollment).

^k CT scans of the chest/abdomen/pelvis scans recommended to be performed 6 months and 1 year after completion of ALL treatments (salvage and adjuvant therapy) (± 2 weeks), and annually for 2 additional years (± 1 month) in patients without evidence of disease progression, otherwise as clinically indicated.

^l Nuclear medicine bone scans recommended to be performed 6 months and 1 year after completion of ALL treatments (salvage and adjuvant therapy) (± 2 weeks), and annually for 2 additional years (± 1 month) in patients without evidence of disease progression, otherwise as clinically indicated.

^m TRUS biopsy must be performed at screening (within 1 year prior to enrollment) only for subjects who have been previously treated with definitive prostate radiotherapy and have disease recurrence in the prostate evidenced by positive molecular imaging (e.g., fluciclovine PET/CT or PSMA PET/CT scan or other per PI discretion).

ⁿ Only for subjects who have been previously treated with an incomplete course of definitive prostate radiotherapy and whose baseline TRUS biopsy is positive. Can be replaced with salvage prostatectomy at the discretion of the treating physician.

^o Only required for subjects with a confirmed lack of PSA response (see section 6.2.3.2) following salvage therapy (see PCWG3 criteria in appendix)

^p Optional blood draws may be performed prior to starting salvage therapy, at the next standard of care follow up visit after completion of salvage therapy, and at the time of confirmed PSA progression or radiological progression. See Section 14.3 for details.

^q After completion of salvage treatment, optional blood will only be collected once at time of confirmed disease progression.

^r Optional archival tissue may be collected at baseline for all subjects for whom it is available. Archival tissue slides should not be cut until requested from the Central Lab. Lack of archival tissue will not be exclusionary.

^s Optional fresh tissue may be collected prior to starting salvage therapy during the TRUS biopsy (if performed) and at the time of oligometastasectomy or prostatectomy (if indicated and if available after SOC tissue collection). See Section 14.1 and 14.2 for details.

^t Quality of life (QOL) questionnaires (FACT-P and Expanded Prostate Cancer Index Composite EPIC-26) will be collected prior to starting salvage therapy, at the Response Assessment Visit, and at each follow-up visits. See Appendices C and D.

^uTo be performed at the Response Assessment Visit and at each follow-up visits See Appendix A

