Statistical Methodology	The planned sample size is N = 20 evaluable subjects. The primary outcome variable of reduction in PSA $\geq 50\%$ at 6 months will be analyzed descriptively via 90% and 95% exact binomial confidence intervals. No hypothesis test will be performed on the primary outcome variables. The sample size is justified by the width of the 95%

	confidence intervals. We anticipate that the PSA 50% response rate at 6 months will be 30% based on the results published by Siriwardana, as their PSA response at 6 weeks and 12 months was 43% and 23% respectively. However, the definition used here is somewhat different than the definition in that clinical study. If the observed PSA 50% response rate is 30% (6/20), the 95% exact binomial confidence interval (Clopper-Pearson) will be 12% to 54 %. With 20 evaluable subjects the maximum width of a 95% exact binomial confidence interval is 46% (27% to 73%) and occurs when the observed response rate is 50% (10/20).
--	---

SCHEMA

Figure 1: Overall Treatment Schema (All Arms)

[figure not shown]
[figure not shown]

Figure 2: Adjuvant radiotherapy (Arms B and C only)

1. With completion of prostate radiotherapy (for patients who received an incomplete definitive radiation course) OR salvage prostatectomy if positive baseline TRUS biopsy (including subjects enrolled in Arm A)
2. Bone radiotherapy can be completed prior to surgical resection if indicated in the opinion of the investigator.
3. Ipsilateral involved-field radiotherapy to 45 Gy in 25 fractions using image-guided IMRT
4. Simultaneous integrated boost to gross target volumes to be ≥ 76 Gy EQD2
5. Target volume defined with inferior dosimetric border set immediately above the previously treated area. Nodal volumes will be treated to 50.4 Gy. The prostate fossa will be treated for post-prostatectomy patients who have not had any radiation to the prostate fossa.

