3.1.2 Salvage Prostatectomy

Subjects previously treated with definitive radiotherapy whose TRUS biopsy is positive for malignancy when screening for the study (see inclusion criterion 5.1.4) must undergo salvage prostatectomy (or salvage radiotherapy if applicable, see Section 3.2.1). This can be done prior to enrollment on the study or at the same time as the nodal dissection described in Section 3.1.1 above.

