3.2.1 Salvage Radiotherapy for Subjects with Positive TRUS Biopsy at Baseline

Subjects previously treated with an incomplete course of definitive radiotherapy (as defined according to institutional standards) who have positive molecular imaging (e.g., fluciclovine PET/CT or PSMA PET/CT scan or other per PI discretion) suggesting recurrent intraprostatic disease and whose TRUS biopsy is positive for malignancy when screening for the study (see inclusion criterion 5.1.4) must undergo completion of their radiation course or salvage prostatectomy as defined in section 3.1.2.

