5.1 Inclusion Criteria

Yes/No (Response of "no" = subject ineligible)

5.1.1 _____ Male subjects age \geq 18 years.

5.1.2 _____ Histologically proven adenocarcinoma of the prostate.

5.1.3 _____ Recurrent prostate carcinoma after definitive therapy for primary disease defined as:

- Post-prostatectomy (with/without adjuvant radiotherapy): Patients must have a detectable or rising PSA level that is >0.05 ng/mL, with a second confirmatory level that is >0.05 ng/mL after a minimum of 1 week.
- Post radiotherapy/ablation (without radical prostatectomy): PSA rise ≥ 2 ng/mL over nadir.

5.1.4 _____ Subjects treated with prior definitive radiotherapy for prostate cancer who have positive molecular imaging (e.g., fluciclovine PET/CT or PSMA PET/CT scan or other per PI discretion) suggesting recurrent intraprostatic disease must undergo TRUS biopsy less than or equal to one year before study enrollment:

- If the TRUS biopsy is negative, no additional treatment is required to the prostate in addition to that of scan-positive sites.
- If the TRUS biopsy is positive, subject must undergo salvage prostatectomy or salvage radiotherapy to the primary site concurrently with the study treatment per the treatment protocol algorithm.
- Note: Biopsy is not required for prostate fossa recurrences after radical prostatectomy.

5.1.5 Oligometastatic disease defined as 10 or fewer metastatic lesions to lymph nodes and/or bones only.

5.1.6 For patients with oligometastatic disease involving lymph nodes, metastasis is confined to the pelvic or para-aortic (below IMA) regions on molecular imaging (e.g., fluciclovine PET/CT or PSMA PET/CT scan or other per PI discretion).

5.1.7 All subjects must be surgical candidates if surgery is indicated per the treatment algorithm.

5.1.8 ECOG Performance Status ≤ 2 .

5.1.9 Use of condoms for male subjects who have not had surgical removal of their prostate and have a partner of child bearing potential beginning at the time of ICF signature and lasting until at least 6 months after the last radiation treatment. Because of the potential side effect on spermatogenesis associated with radiation, female partners of childbearing potential must agree to use a highly effective contraceptive method during and for 6 months after completing treatment.

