9.2.1 Salvage Therapy

- Oligometastasectomy for subjects with nodal metastases (Arms B or C, without or with bone metastases).
 - Subjects who have received a full course of definitive prostate radiotherapy and whose TRUS biopsy is positive at screening (or less than or equal to one year before enrollment) can undergo simultaneous salvage prostatectomy, or, if their initial dose of radiation was felt to be insufficient, complete a course of salvage prostate radiotherapy.
 - Some optional tissue resected during the procedures (oligometastasectomy and/or prostatectomy) may be collected for correlative research purposes if available after SOC tissue collection.
- SBRT (or hypofractionated RT) for subjects with bone metastases only (Arm A).
- For subjects with both nodal and bone metastases, surgery will take place on Day 1 and SBRT will follow once the subject has recovered from surgery. (Arm C)

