11.2.2 Evaluable for response

Patients are only evaluable if they complete their designated intervention:

- Patients on Arm A must complete at least 70% of planned radiation treatments;
- Patients on Arm B must complete surgery;
- Patients on Arm C must complete surgery and at least 70% of planned radiation treatments.

Patients that are unevaluable for response will be replaced.

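### Calendar footnotes n and xiv, Section 9.2.1 and the Arm A and Arm B calendar rows conflict with the sections that require salvage prostate treatment after a positive biopsy

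*Combined protocol and SAP*

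**What the plan says.** Four places in the combined protocol and SAP treat a positive biopsy after definitive radiotherapy as a trigger for prostate treatment.

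- Section 5.1.4: "If the TRUS biopsy is positive, subject must undergo salvage prostatectomy or salvage radiotherapy to the primary site concurrently with the study treatment". It sets no limit by arm or by completeness of the earlier course.
- Section 3.1.2: such subjects "must undergo salvage prostatectomy (or salvage radiotherapy if applicable, see Section 3.2.1"). Section 3.2.1 covers those whose earlier course was incomplete; they "must undergo completion of their radiation course or salvage prostatectomy as defined in section 3.1.2".
- Section 6.2.1 (nodal disease, so Arms B and C) has prostatectomy performed with the dissection unless salvage radiotherapy is indicated under 3.2.1.
- Schema footnote 1 gives completion of radiotherapy or salvage prostatectomy, "including subjects enrolled in Arm A".

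Three places differ.

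- Footnote n (Arm B calendar) and footnote xiv (Arm C calendar), both attached to the salvage prostatectomy row: "Only for subjects who have been previously treated with an incomplete course of definitive prostate radiotherapy and whose baseline TRUS biopsy is positive". A second sentence lets the physician substitute salvage prostatectomy.
- Section 9.2.1 says that full-course, biopsy-positive subjects "can undergo simultaneous salvage prostatectomy" or, if the initial dose was judged too low, have salvage prostate radiotherapy.
- Section 6.1 and the Arm A calendar contain bone radiotherapy only. The Arm B calendar has a prostatectomy row but no prostate radiotherapy row; the Arm C calendar has both.

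**The concern.** The same subject gets different instructions depending on the page consulted. The primary endpoint is a fall of at least 50% in total PSA six months after all treatment, and biopsy-proven disease in the prostate is a plausible source of PSA. Whether it is treated could therefore decide whether that subject counts as a responder.

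In Arms B and C there is a second route. Under Section 6.2.3 the PSA change after salvage therapy decides whether adjuvant nodal radiotherapy is given, and a fall of less than one third is classed as failure with no adjuvant treatment. A difference in prostate treatment could thus carry through to later treatment. The trial's stated purpose is a reference response rate, and that requires a reader to know what treatment the rate describes.

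**Working it through.** This is mainly a comparison of passages. The index subject has prior definitive radiotherapy, positive intraprostatic imaging and a positive TRUS biopsy.

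| Source | Full earlier course | Incomplete earlier course | Arm A |
|---|---|---|---|
| 5.1.4 | Required, either modality | Required, either modality | Not excluded |
| 3.1.2 with 3.2.1 | Prostatectomy required | Completion of radiotherapy or prostatectomy required | Not excluded |
| 6.2.1 | Prostatectomy, unless radiotherapy indicated under 3.2.1 | Same | Not applicable |
| Schema footnote 1 | Prostatectomy | Completion of radiotherapy or prostatectomy | Expressly included |
| 9.2.1 | Permitted | Not addressed | Not addressed |
| Footnotes n, xiv | Prostatectomy excluded | Prostatectomy, replaceable by prostatectomy | Not applicable |
| 6.1 and Arm A calendar | n/a | n/a | No prostate step |

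**Arms B and C, full course.** Prostatectomy is required or offered by the first four rows, permitted by 9.2.1 and excluded by the footnotes. In Arm C, footnote xv restricts the prostate radiotherapy row in the same way, so the calendar read literally leaves this subject with neither modality. In Arm B there is no prostate radiotherapy row at all.

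**Arm A.** Section 5.1.4 and the schema footnote call for prostate treatment, but 6.1 and the calendar provide no step for it.

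**Likely origin.** Footnotes n and xiv match footnote xv word for word. On the prostate radiotherapy row the substitution sentence makes sense; on the prostatectomy row it is circular. The text was probably copied from one row to the other.

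**Plan's own figures.** The exact 95% limits are Beta⁻¹(0.025; x, n−x+1) and Beta⁻¹(0.975; x+1, n−x). With n = 20:
- x = 6: 11.9% to 54.3%, matching the stated 12% to 54%.
- x = 10: 27.2% to 72.8%, width 45.6 points, matching the stated 27% to 73% and 46%.

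The sample-size figures are correct and unaffected by this point.

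**Sensitivity per subject.** One changed response moves the rate by 1/20 = 5 points. From 6/20 (30%), one fewer gives 5/20 = 25% (8.7% to 49.1%), and one more gives 7/20 = 35% (15.4% to 59.2%).

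**Illustration under assumptions.** The documents give neither the number of affected subjects, k, nor their response rate, p. If the other 20−k respond at 30%, the expected rate is [(20−k) × 0.30 + k × p]/20.
- k = 0: 30%.
- k = 1, p from 0 to 0.60: 5.7/20 = 28.5% to 6.3/20 = 31.5%.
- k = 3, same p: 5.1/20 = 25.5% to 6.9/20 = 34.5%.

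These values of k and p are chosen only to show scale.

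**The case against.** The best case against is that most of the protocol agrees. Sections 5.1.4, 3.1.2, 3.2.1 and 6.2.1 and the schema footnote point the same way, and the investigator signs an eligibility checklist that contains 5.1.4. A footnote that replaces an operation with itself cannot be followed as written and would send the reader back to the text. In 9.2.1 the permissive verb may concern only modality and simultaneous timing, because 3.1.2 says of prostatectomy: "This can be done prior to enrollment on the study or at the same time as the nodal dissection".

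Much of this stands. It makes the problem a set of outlying passages rather than general disagreement, and it makes 9.2.1 weak evidence that treatment is optional. It does not remove the conflict. No order of precedence is stated, and a copying error explains the footnotes without correcting them. Surgery before enrollment does not settle Arm A either: 5.1.4 ties treatment to the study treatment, and the other timing in 3.1.2 is the nodal dissection, which Arm A does not have.

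Three stronger readings are tempting but unsupported.

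- *That affected subjects will go untreated because staff work from the calendar.* Nothing in the documents says so; this is one possible misreading of the plan.
- *That the bias can be sized by assuming several affected subjects at 5 points each.* That is a ceiling, reached only if every one of them changes response status, and the count has no source.
- *That the evaluability rule in 11.2.2 overlooks prostate treatment and should require it.* The rule is unspecific (for example, "Patients on Arm A must complete at least 70% of planned radiation treatments"), but its references to surgery and planned radiation can be read to include the prostate. Adding a requirement would also widen exclusion and replacement of subjects after enrollment, which is a separate and debatable change.

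**Conclusion.** The inconsistency is real and needs correcting. Footnotes n and xiv state a restriction that contradicts 5.1.4, 3.1.2 and 6.2.1; 9.2.1 is looser than those sections; and the Arm A material and the Arm B calendar lack steps that other passages call for. The possible effect on PSA response and on adjuvant selection is a reasonable inference, resting on the assumption that treating biopsy-proven prostate disease can alter total PSA. It is bounded per subject at 5 points, could be zero overall, and has no computable net size. The affected group is narrow: biopsy-positive subjects with a full earlier course in Arms B or C, any biopsy-positive subject in Arm A, and Arm B subjects for whom prostate radiotherapy is the chosen option. The schema figures are not available, so only the schema footnotes were checked. No view is taken on which clinical rule is right.

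**What to change.** In one amendment, reconcile footnotes n and xiv, the intervention rows of the Arm A and Arm B calendars, and Sections 6.1 and 9.2.1 with Sections 5.1.4, 3.1.2, 3.2.1 and 6.2.1 and schema footnote 1. All should name the same subjects, by arm and by completeness of the earlier course, and state the same requirement. Remove the circular substitution sentence from the prostatectomy footnotes. The sponsor decides which clinical rule applies.

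The cost is protocol and calendar wording and one amendment submission. The sample size, the primary analysis and the evaluability rule need no change on this account.
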